Appendix D. Modified Immune-Related Response Criteria in Solid Tumors (irRECIST)

The Immune-related Response Criteria (irRC) based on bidimensional measurements were derived from WHO/RECIST to serve as guidelines to systematically characterize additional patterns of response in patients with advanced melanoma receiving ipilimumab therapy and to allow the potential delayed clinical response to immune-enhancing therapies to be captured more accurately (Wolchok JD et al., 2009). Recent evaluation showed that irRC using unidimensional measurements provided highly concordant tumor response assessment and less measurement variability compared with bidimensional measurements (Nishino M et al., 2013). This study will utilize a modified criteria (irRECIST), adapting the immune-related response criteria to conventional RECIST 1.1 (Eisenhauer et al, 2009) as outlined below.

Antitumor response based on total measurable tumor burden

- For irRECIST, only index and measurable new lesions are taken into account (in contrast to conventional RECIST 1.1, which does not require the measurement of new lesions, nor do they include new lesion measurements in the characterization of evolving tumor burden).

Tumor burden assessment:

- All measurable and non-measurable lesions should be assessed at screening and at the defined tumor assessment time points.
 - At baseline tumor assessment: tumor burden is the sum of the longest diameters (SLD) of all index lesions (5 lesions per organ, up to 10 total lesions).
 - At each subsequent tumor assessment: tumor burden is the SLD of the index lesions and of new, measurable lesions (≥ 10 mm in the longest diameter; up to 5 new lesions per organ and up to 10 total lesions) added together
 - Tumor burden = $SLD_{\text{index lesions}} + SLD_{\text{new, measurable lesions}}$

Time point response assessment using modified irRECIST

Percentage changes in tumor burden per assessment time point describe the size and growth kinetics of both conventional and new lesions as they appear. At each tumor assessment, the response in index and new measurable lesions is defined based on the change in tumor burden (after ruling out irPD). Decreases in tumor burden must be assessed relative to baseline measurements (ie, the SLD of all index lesions at screening).

Definitions:

- Methods of measurement:
 - The same imaging modality, method of assessment, and technique must be used throughout the study to characterize each identified and reported lesion.
 - MRI or CT scans should be performed with contiguous slice thickness of 5 mm or less according to the Imaging Manual. Subjects should be evaluated at screening for tolerance to MRI/CT IV contrast. Subjects intolerant of CT IV contrast ie, allergy or renal insufficiency should be imaged using non-contrast CT for the chest and MRI (with or without contrast) for the abdomen and pelvis to enable the best detection of disease throughout the study starting at baseline. If a subject develops a medical contradiction to the MRI/CT IV contrast while on study, preapproval of the sponsor is needed to switch from contrast enhanced MRI to non-contrast MRI or to CT (and vice versa).
 - If a combined PET/CT scan is performed at the discretion of the investigator at baseline and subsequent timepoints, the CT portion of that exam should not be substituted for the dedicated diagnostic CT exams required by this protocol unless the investigator or the site radiologist can document that the CT performed as part of a PET/CT is of identical diagnostic quality to the diagnostic CT as described in the Imaging Manual, then the CT portion of the PET/CT can be used for tumor measurements.
 - Pathological lymph nodes (short axis >10 mm) should be assessed by MRI/CT. Only nodes with short axis ≥ 15 mm are to be included as measurable lesions.
 - Patients with suspected brain metastases will also undergo MRI of the brain.
 - All baseline evaluations should be performed as closely as possible to the beginning of treatment, and not more than 28 days before the beginning of the treatment (cycle 1 day 1).
- Measurable disease: Subject must have radiographically measurable disease per RECIST 1.1 ([Eisenhauer et al, 2009](#)).
 - Measurable lesions:
 - Lesions with clear borders that can be measured accurately in one dimension (longest diameter ≥ 10 mm as measured by MRI/CT with scan slice thickness ≤ 5 mm).
 - Pathologic lymph nodes are measurable when the longest diameter perpendicular to the long axis (short axis) is ≥ 15 mm on MRI/CT.
 - Must exclude cystic lesions, pleural/pericardial effusions and ascites.
 - Non-Measurable lesions:
 - All other lesions, including small lesions (longest diameter < 10 mm or pathological lymph nodes with ≥ 10 mm but < 15 mm short axis) and other truly non-measurable lesions are considered non-measurable and characterized as non-index lesions.

- Only cancerous lesions should be selected as non-measurable lesions and not indeterminate lesions and lesions that could be cancer. Other examples of non-measurable lesions include some bone lesions*, leptomeningeal disease, inflammatory breast disease, lymphangitic involvement of the skin or (lymphangitis cutis/pulmonis), and groups of lesions that are small and numerous.
- Fluid collections
 - Ascites, pleural effusion, or pericardial effusion, should not be selected as non-measurable disease at baseline or, if new or increased, as evidence of progressive disease. These collections may occur with both benign and malignant conditions, and their etiology is often not clear. These collections may often be removed via interventional procedures, which can lead to a false interpretation of disease response. Thus, these fluid collections should not be used as a baseline non-index or as evidence of disease response.
- Bone Lesions
 - Bone scans, PET scans or plain films are not considered adequate imaging techniques to measure bone lesions. However, these techniques can be used to confirm the presence or absence of bone lesions.
 - Osteolytic (lytic) bone lesions or mixed lytic-blastic lesions, with identifiable soft tissue components, that can be evaluated by cross-sectional imaging technique such as CT or MRI can be considered as measurable lesions if the soft tissue component meets the definition of measurability described above. Only the soft tissue component of the bone lesion should be measured.
 - Many osteoblastic (blastic) bone abnormalities can be benign and should not be selected as baseline lesions. An isolated new small blastic lesion should not be selected as a new lesion unless there is demonstrated growth on subsequent scans. Multiple new blastic lesions that are clearly cancerous may be considered for new lesions.
- Cystic lesions:
 - Lesions that meet the criteria for radiographically defined simple cysts should not be considered as malignant lesions (neither measurable or non-measurable) since they are, by definition, simple cysts.
 - Cystic lesions thought to represent cystic metastases can be considered as measurable lesions, if they meet the definition of measurability described above. However, if non-cystic lesions are present in the same subject, these are preferred for selection as index lesions. If a cystic lesion is clearly cancerous and has both cystic and solid components, then the complete lesion should be measured including both components without excluding the cystic portion of a cystic tumor lesion when measuring.

- Lesions with prior local treatment:
 - Tumor lesions situated in a previously irradiated area, or an area subject to other loco-regional therapy, should not be considered measurable unless there has been demonstrated progression in the lesion.
- Index lesions: all measurable lesions up to a maximum of 5 lesions per organ and 10 lesions in total, representative of all involved organs, are to be identified as Index lesions, recorded and measured. Index lesions are to be selected on the basis of their size and their suitability for accurate repeated measurements by imaging, and most representative of the subject's tumor burden and overall disease status.
- New lesions: New measurable lesions (ie, accurately and serially measurable in at least 1 dimension ≥ 10 mm for non-nodal lesions or the short axis is ≥ 15 mm for nodal lesions). The new measurable lesions should be selected on the basis of their size and suitability for accurate repeated measurements by CT or MRI. If there are more than 10 measurable new lesions detected at an imaging time point for a subject, lesions not selected for measurements would be considered non-Index lesions.
- Non-Index lesions: measurable lesions, other than index lesions, and all sites of non-measurable disease, will be identified as non-index lesions. Non-index lesions will be evaluated at the same assessment time points as the index lesions. In subsequent assessments, changes in non-index lesions will contribute only in the assessment of complete response.
 - Pathologic lymph nodes with short axis ≥ 10 mm but < 15 mm at baseline should be considered as non-index lesions
- Unable to evaluate (UE): Any lesion present at baseline which was not assessed or was unable to be evaluated leading to an inability to determine the status of that particular tumor for that time point
- Not Available (NA): Scan not available
- Not Done (ND): Radiographic imaging were not performed at this time point to evaluate the index lesions
- Merging lesions:
 - When two or more index lesions merge, the smaller lesion should have 0 mm recorded for the current and all future assessments, and the larger lesion should have the longest diameter of the merged lesion recorded for the current assessment and be followed for future assessments.
- Separating lesions:
 - When an index lesion splits into 2 or more lesions, the largest measurable part of the split lesion should be considered to be the previously recorded index lesion with measurements provided for the current assessment and followed for future assessments. The remaining lesions would be non-index lesions. Any new lesions that result from separating should be documented as non-index lesions that were generated by separating and not truly new lesions.

- Index lesion response
 - Immune-related Complete Response (irCR) – complete disappearance of all index lesions in two consecutive observations at least 4 weeks apart
 - Pathologic lymph nodes must have reduction in short axis to < 10 mm
 - Immune-related Partial Response (irPR) – decrease of 30% or greater in tumor burden compared with baseline in two consecutive observations at least 4 weeks apart
 - Immune-related Stable Disease (irSD) - not meeting the criteria for irCR or irPR, in the absence of immune-related progressive disease
 - Immune-related Progressive Disease (irPD) – at least a 20% increase in tumor burden compared with nadir (at any single time point) in two consecutive observations at least 4 weeks apart
 - When the size of the tumor lesion is considered ‘too small to measure’ (eg, less than 5 mm), a default value of 5 mm should be assigned for index lesions. If this is nadir, irPD will be judged from the tumor burden calculated using the default value.
- Non-Index Lesion Response
 - irCR – complete disappearance of all non-index lesions.
 - Pathologic lymph nodes must have reduction in short axis to < 10 mm
 - irPR and irSD – non-Index lesions are not considered in the definition of irPR or irSD. Measurements of non-index lesions are not required, but they are evaluated at each timepoint as ‘present’, ‘absent’ or ‘unequivocal progression’. If a significant partial response is observed in a non-index lesion, it should be described as a comment.
 - irPD – increases in number or size of non-index lesion(s) does not constitute progressive disease. New lesions that are measurable up to 5 new lesions per organ and 10 total) are included in the calculation of tumor burden in response assessments
- Overall response
 - irCR – complete disappearance of all lesions (whether measurable or not, and no new lesions)
 - Confirmation by a repeat, consecutive assessment no less than 4 weeks from the date of the first documented response
 - irPR – decrease in tumor burden \geq 30% relative to baseline.
 - Confirmation by a repeat, consecutive assessment no less than 4 weeks after the first documentation
 - irSD – not meeting criteria for irCR or irPR, in the absence of irPD
 - irPD – increase in tumor burden \geq 20% relative to nadir (minimum recorded tumor burden) and at least 5 mm absolute increase compared to nadir.
 - Confirmation by a repeat, consecutive assessment no less than 4 weeks from the date of the first documented assessment.

Response confirmation:

- irCR and irPR:
 - the repeat confirmation scan may be performed any time after 4 weeks from the first suspected radiologic evidence of response and may be delayed until the next scheduled scan to avoid necessary procedures
- irPD:
 - In subjects who have initial evidence of radiological PD by irRECIST (irPD on one scan), it is at the discretion of the PI whether to continue a subject on study treatment until repeat imaging is obtained based on their assessment of clinical stability. Subjects may receive study treatment and tumor assessment should be repeated ≥ 4 weeks later in order to confirm irPD per site assessment.
 - In determining whether or not the tumor burden has increased or decreased per irRECIST, the local site investigator should consider all index as well as any incremental new measureable lesion(s).
 - irPD is confirmed at repeat imaging (irPD on two consecutive scans at least 4 weeks apart) if tumor burden remains $\geq 20\%$ and at least 5 mm absolute increase compared to nadir
 - Subjects with a global deterioration of health status requiring discontinuation of treatment without radiographic confirmation of disease progression (confirmed irPD) at the time should have the reason for treatment discontinuation classified as 'clinical disease progression'. In this case, irPD cannot be assigned at the time as the overall objective tumor response. Every effort should be made to radiographically confirm irPD even after discontinuation of treatment.

Measurement and Tumor Response Assessment Based on modified irRECIST	
Measurable lesions	
 • ≥ 10 mm (unidirectional measure) • Pathologic lymph nodes: short axis ≥ 15 mm
Measurement of each lesion	The longest diameter (mm)
The sum of the measurements (SLD)	
 • The sum of the longest diameters (SLD) of all index lesions and new measurable lesions, if any • Up to 5 lesions per organ, up to 10 total
Response assessment	
 • irPD: $\geq 20\%$ increase from nadir and at least 5 mm absolute increase compared to nadir (requires confirmation) • irSD: $< 30\%$ decrease from baseline and $< 20\%$ increase from nadir • irPR: $\geq 30\%$ decrease from baseline (requires confirmation) • irCR: Disappearance of all lesions (requires confirmation)
New Lesions	The presence of new lesion(s) does not define progression. Measurable new lesions (≥ 10 mm): The measurements of the new lesions(s) are included in the SLD
Confirmation	Confirmation by 2 consecutive observations at least 4 weeks apart required for irCR, irPR and irPD.

Modified irRECIST Overall Response Assessment			
Measurable Response	Non-measurable Response		Overall Response
Index and new measurable lesions (tumor burden) ^a , %	Non-Index lesions	New non-measurable lesions	Using irRECIST
↓ 100%	Absent	Absent	irCR ^b
↓ 100%	Stable/NA	Any	irPR ^b
↓ 100%	Unequivocal progression	Any	irPR ^b
↓ $\geq 30\%$	Absent/Stable/NA	Any	irPR ^b
↓ $\geq 30\%$	Unequivocal progression	Any	irPR ^b
↓ $< 30\%$ to ↑ $< 20\%$	Absent/Stable/NA	Any	irSD
↓ $< 30\%$ to ↑ $< 20\%$	Unequivocal progression	Any	irSD
↑ $\geq 20\%$	Any	Any	irPD ^b
UE	Any	Any	UE
ND	Any	Any	UE
NA	Any	Any	UE

NA = not available; ND = not done; UE = unable to evaluate

^a Decrease assessed relative to baseline, including new measurable lesions (≥ 10 mm)

^b Response (irCR, irPR) and progression (irPD) are confirmed by a second, consecutive assessment at least 4 weeks apart.

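### Appendix D scores nodal complete response by short axis but sums longest diameters and requires a 100% fall for overall irCR, so a normalised node that is still visible cannot score irCR, and in node-dominant disease can score irSD

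*Protocol*

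**What the plan says.** All of the rules below are in Protocol Appendix D.

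- **What is summed.** Under Tumor burden assessment, at baseline "tumor burden is the sum of the longest diameters (SLD) of all index lesions". At follow-up "tumor burden is the SLD of the index lesions and of new, measurable lesions". The summary table repeats this: "The sum of the longest diameters (SLD) of all index lesions and new measurable lesions, if any". Its row on how each lesion is measured names the longest diameter only. The cap is 5 lesions per organ and 10 in total.
- **When a node is measurable.** Under Methods of measurement, "Only nodes with short axis ≥ 15 mm are to be included as measurable lesions". The definitions of measurable and of new lesions, and the measurability row of the summary table, carry the same 15 mm short-axis limit.
- **When a node counts as completely responding.** Under Index lesion response, as a sub-bullet of irCR, "Pathologic lymph nodes must have reduction in short axis to < 10 mm". The same line appears under Non-Index Lesion Response.
- **When the subject counts as irCR.** The Overall response text requires every lesion to disappear and does not repeat the nodal rule. The overall-response table requires a 100% decrease in tumor burden. A decrease of at least 30% is irPR. A decrease of less than 30% with an increase of less than 20% is irSD.

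No line says which axis of a node enters the sum, or that a node below 10 mm short axis counts as zero or absent in the table. The only default given is 5 mm for index lesions too small to measure.

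The irRECIST ORR is the primary efficacy endpoint (Protocol 10.1.1.1). Stage 2 recommendations use local irRECIST (Protocol 10.3.1; SAP 8.1), and the SAP analyses investigator-reported data (SAP 10.6.1).

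**The concern.** A lymph node that returns to normal size is still a visible structure with a long axis. If that long axis stays in the sum, the sum cannot fall by 100%. The lesion-level rule then calls the node a complete response while the subject-level table cannot return irCR. If nodes are most of the measured disease, the fall in the sum may also miss 30%, and the table returns irSD.

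The conflict is therefore between the lesion-level definition on one side and the overall-response text and table on the other. Where it reaches irSD, it decides whether a subject counts in the primary ORR. In Groups 2, 4a and 4b the stage 1 recommendation turns on none versus at least one responder in 10, so one subject could matter. SAP 10.10 drops RECIST 1.1 because the data were not collected, so the planned analyses contain no second response criterion to expose a misclassification.

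**Working it through.** The plan states no figure for this point. The check applies the two sets of Appendix D rules to the same nodes. The node sizes are illustrative. Each case has no other lesions and assumes confirmation at least 4 weeks later.

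Formula: change in sum = (follow-up sum / baseline sum) - 1, compared with -100% (irCR), -30% (irPR) and +20% (irPD).

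| Long x short axis, mm | Index-lesion rule | Sum of longest diameters | Table | Sum of short axes |
|---|---|---|---|---|
| 30x16 to 22x9 | irCR | 22/30 - 1 = -26.7% | irSD | 9/16 - 1 = -43.8% |
| 22x15 to 17x9 | irCR | 17/22 - 1 = -22.7% | irSD | 9/15 - 1 = -40.0% |
| 24x16 + 20x15 to 18x9 + 15x8 | irCR | 33/44 - 1 = -25.0% | irSD | 17/31 - 1 = -45.2% |
| 20x16 to 13x9 | irCR | 13/20 - 1 = -35.0% | irPR | 9/16 - 1 = -43.8% |

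No case reaches irCR in the table. The last row shows that node-only disease does not always fall to irSD.

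**Mixed disease.** Let w be the nodal share of the baseline sum and s the fractional shrinkage of the nodal long axis, with all non-nodal lesions gone. The total decrease is (1 - w) + w·s. It is below 30% only if w > 0.70/(1 - s):

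- s = 10%: w above 0.70/0.90 = 77.8%
- s = 20%: w above 0.70/0.80 = 87.5%
- s = 25%: w above 0.70/0.75 = 93.3%

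Below these shares the table gives irPR, and the subject is a responder either way.

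**Short-axis sum.** A node going from 15 mm or more to below 10 mm falls by more than 1 - 10/15 = 33.3%, so it always passes the 30% cut-off. It still does not fall by 100%, so changing the axis alone does not repair the irCR row.

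**Possible effect on power (assumption only).** An exact two-stage binomial calculation, summing over stage 1 counts above the futility limit, reproduces the stated 80% power: 0.800 for Group 1, 0.801 for Groups 2, 4a and 4b, and 0.801 for Group 3. The type I error is 0.048, 0.047 and 0.048 respectively. Suppose a fraction f of true responders is scored irSD, so the target ORR becomes p1(1 - f):

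| f | Group 1 (p1 = 25%) | Groups 2, 4a, 4b (20%) | Group 3 (30%) |
|---|---|---|---|
| 2% | 0.782 | 0.788 | 0.778 |
| 5% | 0.753 | 0.768 | 0.740 |
| 10% | 0.697 | 0.730 | 0.667 |

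The documents give no value for f.

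**The case against.** The best defence is that the overall-response text and table agree with each other, that criteria labelled as modified may sum longest diameters, and that ORR counts irCR and irPR alike. These points limit the effect on ORR, and most subjects with nodal lesions would keep their responder status. They do not explain what the sub-10 mm rule is for if it never carries through to the overall response.

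A second defence is that "Pathologic lymph nodes are measurable when the longest diameter perpendicular to the long axis (short axis) is ≥ 15 mm on MRI/CT" makes the short axis a node's own longest diameter for summing. That sentence defines measurability only, and the summing rule does not refer to it. The Imaging Manual, which is not available here, may hold a nodal rule. If so, Appendix D should state it.

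Several stronger readings are tempting but not supported:

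- **New small nodes could be scored as progression.** The follow-up summing bullet gives only a 10 mm longest-diameter limit, so a reader might add a new 16 x 8 mm node to a 60 mm nadir (16/60 = +26.7%) and call irPD. But that bullet covers measurable lesions, and the New lesions definition separates the limit "for non-nodal lesions or the short axis is" at least 15 mm for nodes. Such a node is not measurable. A cross-reference is all that is missing.
- **Any nodal index lesion endangers the ORR.** The mixed-disease shares above show otherwise. The proportion of NSCLC subjects in the trial is no measure of node-dominant disease.
- **Investigators will disagree, or one subject decides a stage 1 outcome.** With the Imaging Manual unseen, disagreement is possible but not shown. The stage 1 limits are recommendations, and the Dose Level Review Team decides on all available data (Protocol 10.2, 10.3.1).

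**Conclusion.** The inconsistency is real and lies in the current text of Appendix D. Followed literally, the table cannot return irCR for a subject whose index node has normalised but remains visible, although the lesion-level rule calls that node a complete response. This reading takes the sub-10 mm rule as defining disappearance for a node, since it would otherwise be redundant.

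The usual result is irPR in place of irCR, which misstates the depth of response but leaves ORR unchanged. Responder status changes only in node-only or strongly node-dominant disease, and then only when the long axis shrinks little enough. In those cases the error lowers the response count and could turn one responder in 10 into none. How often this would occur is unknown. The power figures show what given rates would cost and do not estimate the rate. The point merits correction because it touches the primary endpoint and can be settled with a few lines of text.

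**What to change.** In Appendix D, reconcile Tumor burden assessment, Index lesion response, Overall response and both tables:

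1. In the Overall response text and the irCR row of the overall-response table, define irCR as all non-nodal lesions absent and all nodes below 10 mm short axis, with no new lesions, in place of a 100% decrease. This step alone removes the direct contradiction.
2. In Tumor burden assessment and the summary table, state that nodes enter the sum by short axis. This matches the appendix's other nodal rules and avoids a jump at the threshold. With longest diameters, 30x16 to 22x10 mm would be irSD (-26.7%), while 1 mm less on the short axis would be irCR. By short axis it is 10/16 - 1 = -37.5%, irPR.
3. In the follow-up summing bullet, add a cross-reference to the 15 mm short-axis rule for new nodes, as a clarification only.
4. If nodes have already been scored, state in the SAP which axis was recorded, and apply the nodal irCR rule when response is derived.

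The cost is wording in Appendix D, the SAP and the matching data-capture and imaging instructions. No new scans are needed, but nodes recorded only by long axis at follow-up would need their short axis read from existing scans. Step 2 changes how the primary endpoint is measured, so it should be documented as such. The rationale for Amendment 2 records that the sponsor had decided to stop investigating the combination, so the remaining benefit is mainly in how the final analysis is derived and reported.

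### Appendix D drops all but the largest fragment of a split index lesion from the tumor burden, so a lesion that divides without shrinking can be scored as a confirmed irPR

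*Protocol*

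**What the plan says.** The rule is under separating lesions in Protocol Appendix D. After a split, "the largest measurable part of the split lesion should be considered to be the previously recorded index lesion", and for the other pieces, "The remaining lesions would be non-index lesions". They cannot return by another route: "Any new lesions that result from separating should be documented as non-index lesions that were generated by separating and not truly new lesions".

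The same appendix defines what counts:

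- Burden on treatment: "tumor burden is the SLD of the index lesions and of new, measurable lesions".
- irPR: "decrease of 30% or greater in tumor burden compared with baseline in two consecutive observations at least 4 weeks apart".
- Non-index lesions and response: "non-Index lesions are not considered in the definition of irPR or irSD". They need not be measured.
- Non-index lesions and progression: "increases in number or size of non-index lesion(s) does not constitute progressive disease". The overall-response table gives irPR for a fall of 30% or more even when non-index lesions progress unequivocally.

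ORR per irRECIST is the primary efficacy endpoint (Protocol Section 10.1.1.1). The SAP analyses investigator-reported response (Section 10.6.1) and defines response by reference to irRECIST with confirmation (Section 6). It adds no rule for split lesions and no sensitivity analysis for them.

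**The concern.** Appendix D means burden to reflect the total measurable tumor, including measurable lesions that appear on study. The splitting rule works against that aim. A 25 mm lesion arising at a new site is added to the sum, while a 25 mm piece of a lesion already being followed is taken out of it. The recorded fall then comes from relabelling tumor. Confirmation does not catch this, because the second scan is read under the same rule and a split that persists confirms itself.

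A false irPR enters the primary ORR and the counts used for the Simon stage 1 recommendations. The retained fragment also sets the nadir, and the other fragments can no longer contribute to irPD, so duration of response and PFS can be biased too.

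**Working it through.** **1. The plan's own figures.** Inputs are from Protocol Section 10.2. With a stop recommended at r1 or fewer responses among n1, and success at r or more among n, P(success) = Σ over x1 > r1 of Bin(x1; n1, p) × P(X2 ≥ r − x1), where X2 ~ Bin(n − n1, p).

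| Group | n1, r1, n, r | p0, p1 | Alpha | Power |
|---|---|---|---|---|
| 1 | 18, 2, 43, 8 | 10%, 25% | 0.0480 | 0.8003 |
| 2, 4a, 4b | 10, 0, 29, 4 | 5%, 20% | 0.0468 | 0.8011 |
| 3 | 19, 3, 55, 13 | 15%, 30% | 0.0477 | 0.8006 |

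The stated 80% power and 5% one-sided alpha are reproduced, on the premise that response is classified without error.

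**2. When a split becomes irPR.** Change = (retained SLD − baseline SLD) / baseline SLD, and irPR needs −30% or lower. If the summed diameter still equals baseline, the fall is the diameter moved to non-index status divided by baseline SLD. The condition is therefore moved diameter ≥ 30% of baseline SLD. For a sole index lesion that is a largest fragment ≤ 70% of baseline diameter. For an even split of one lesion among several, 0.5 × share ≥ 0.30, so the lesion must hold at least 60% of the burden.

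Lesion sizes below are illustrative.

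| Baseline index lesions (mm) | The 60 mm lesion becomes | SLD and change, Appendix D | SLD and change, all fragments |
|---|---|---|---|
| 60 | 35 + 25 | 35, −41.7%, irPR | 60, 0% |
| 60 | 42 + 18 | 42, −30.0%, irPR | 60, 0% |
| 60 | 43 + 17 | 43, −28.3%, irSD | 60, 0% |
| 60 | 40 + 30 | 40, −33.3%, irPR | 70, +16.7% |
| 60, 20 | 35 + 25 | 55, −31.25%, irPR | 80, 0% |
| 60, 40 | 30 + 30 | 70, −30.0%, irPR | 100, 0% |
| 60, 40 | 35 + 25 | 75, −25.0%, irSD | 100, 0% |

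**3. After the split.** With a 35 mm nadir, irPD is reached when the retained fragment is 35 × 1.2 = 42 mm. The other fragment can grow from 25 to 50 mm, making the total 35 + 50 = 85 mm (+41.7% on 60), with no effect on the recorded burden. Conversely, growth of the retained piece to 42 mm alone meets the irPD threshold when the total is 42 + 25 = 67 mm, only +11.7% on 60. The bias in progression can go either way.

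**4. Stage 1, Groups 2, 4a and 4b.** Let m be the share of true non-responders scored irPR through splitting. This is an assumption; the documents give no rate. The apparent ORR at the null is q = 0.05 + 0.95m, and P(at least 1 of 10) = 1 − (1 − q)^10.

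| m | q | P(escape the 0/10 recommendation) | Two-stage alpha |
|---|---|---|---|
| 0 | 0.0500 | 0.401 | 0.0468 |
| 1% | 0.0595 | 0.459 | 0.0782 |
| 2% | 0.0690 | 0.511 | 0.1178 |
| 3% | 0.0785 | 0.559 | 0.1646 |

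The rise in stage 1 passage is about 6 to 16 percentage points. For the same m of 1%, 2% and 3%, alpha becomes 0.0721, 0.1027 and 0.1395 in Group 1, and 0.0683, 0.0942 and 0.1255 in Group 3. All of these depend on m.

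**The case against.** The case against is mostly about size, and much of it stands.

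- **The examples are favourable to the concern.** They need few index lesions and fragments lying end to end. Up to 10 index lesions are followed, which dilutes the effect, and a split along the long axis can leave the longest diameter almost unchanged. A lesion rarely separates without losing some tissue.
- **No splitting rate is given**, so nothing in step 4 is an estimate.
- **There are safeguards.** Remaining fragments block irCR. Stage 1 rules are recommendations, and the DLRT decides on all available data (Protocol Section 10.3.1). Scans go to a core laboratory and may be re-read (Section 7.4). The Imaging Manual, which is outside these documents, might add a rule. The SAP's TTP counts clinical progression, so fragment growth is not wholly hidden there.
- **Leaving non-index growth out of irPR and irPD is a general feature of Appendix D.** What is particular to splitting is that tumor already in the baseline sum is moved into that category.
- **Summing diameters can err the other way.** A 60 mm lesion dividing lengthwise into 58 and 55 mm would sum to 113 mm (+88%) without growth. Counting only fragments of 10 mm or more would also leave a gap: 42 + 9 + 9 mm would still score −30%. The remedy has to deal with both.
- **Stage 1 now carries little practical weight.** The rationale for Amendment 2 says the sponsor has decided to stop investigating the combination, and the SAP covers the final analysis. The reported irORR remains.

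None of this puts the fragments back into the primary ORR as the documents define it.

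**Conclusion.** The rule gives a wrong result as written. A subject with no reduction in summed diameter can be counted as a confirmed irPR in the primary ORR, subject to the condition in step 2. The mechanism follows directly from the text. Its frequency, and so the bias, is unknown. The correction is worth making, but the documents do not show that the ORR will be materially wrong.

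Four stronger readings might be inferred and are not supported:

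- **That 70% of the previous diameter is the trigger.** irPR is judged against baseline. A 60 mm lesion that grows to 80 mm and splits into 50 and 30 mm keeps 50/80 = 62.5% of its prior diameter but 50/60 = 83.3% of baseline, which is not irPR. A split accompanied by real shrinkage is also not necessarily a false response.
- **That a 1-3% rate adds 10-26 points to the chance of passing stage 1.** The figure 1 − (1 − m)^10 gives 9.6% to 26.3% for at least one false responder in 10. A group at the 5% null already passes 40% of the time, so the added chance is the smaller one in step 4.
- **That the merging rule shows burden is otherwise conserved.** It does say "the larger lesion should have the longest diameter of the merged lesion recorded for the current assessment", but it also sets the smaller lesion to 0 mm from then on. Two 30 mm lesions joining side by side as 35 mm would score (35 − 60)/60 = −41.7%.
- **That fragments rejoining must produce a false irPD** (60/35 − 1 = +71%). The merging rule covers index lesions and the fragments are non-index, so no rule addresses this case.

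**What to change.** Replace the separating-lesions paragraph in Appendix D so that:

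- all fragments stay under the original index lesion and are not reclassified as non-index;
- the value recorded for that lesion, at this and every later assessment, is the sum of its fragments' longest diameters, including fragments under 10 mm, with the appendix's existing 5 mm default for any too small to measure;
- fragments do not count against the limits of 5 lesions per organ and 10 in total;
- an increase due only to splitting is flagged and is not by itself read as growth, because a lengthwise split can overstate the sum.

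For assessments already made, pre-specify in the SAP a sensitivity irORR that restores the fragments in every subject with a recorded split, alongside the primary irORR. The rule already asks for such fragments to be documented as arising from separation, so the subjects should be identifiable.

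**Cost.** Going forward: one paragraph, matching CRF and imaging instructions, and a few extra measurements on the same scans by the same reader. Looking back, the cost is higher. Non-index fragments did not have to be measured, so affected subjects need a re-read of scans already sent to the core laboratory. That work is confined to subjects with a recorded split. Some judgement remains for lengthwise splits.
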